Study Title: The impact of price promotions on purchases of confectionery and snacks: a randomised controlled trial in an experimental online supermarket study

Med IDREC Ref: R65010/RE005

Date 02/12/2021 Version 1.0

Summary of study

Participants (n=500) were asked to imagine they were buying snacks for a night in with 4 friends, with a budget of £5-£10. They were asked to select products from:

- Confectionery
- Biscuits and crackers
- Crisps, nuts and snacking fruit
- Cakes and tarts

They were randomised to one of two groups:

1. Promotions removed: No promotions present on any products
2. Promotions included: Promotions applied to a pre-determined percentage of food products (matching frequency/discount depth found on real online supermarket) within the target categories listed above.

Primary Analysis

Linear regression models will compare the total energy (kcal) purchased in the two groups. Any baseline variables (e.g. demographic characteristics) which appear to have been imbalanced between groups will be adjusted in the model. If no baseline characteristics are needed in models, then simpler t-tests will be considered. Non-parametric equivalents will be used should assumptions for parametric tests be violated.

Sensitivity analysis:

The primary analysis will be run including only participants who spent between £5 and £10 on products from the target categories (Confectionery; Biscuits and crackers; Crisps, nuts and snacking fruit; Cakes and tarts) will be included, to explore the impact for participants who had greater likelihood of being exposed to the promotional activity.

Secondary Outcomes

Linear regression models will compare the two groups on:

- a. total sugar (g, kcal, %E)
- b. total salt (g, kcal, %E)
- c. total saturated fat (SFA) (g, kcal, %E)

Secondary Analyses

1. *Including demographics:* Linear regression models will compare purchases in the two groups, stratified by demographic covariates including gender, age group, ethnic group (White vs Non-White), BMI (<30 and $\geq 30\text{kg}/\text{m}^2$) groups, education level (lower vs. higher), and household income (lower vs. higher) [provided we have sufficient numbers within each subgroup ($n \geq 30$)], with the following outcomes:
 - a. total energy (kcal)
 - b. total sugar (g, kcal, %E)
 - c. total salt (g, kcal, %E)
 - d. total SFA (g, kcal, %E)

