2. *By food category:* Linear regression models will also compare differences in purchasing for each of the individual target categories (Confectionery; Biscuits and crackers; Crisps, nuts and snacking fruit; Cakes and tarts) separately, in:
 - a. total energy (kcal)
 - b. total sugar (g, kcal, %E)
 - c. total salt (g, kcal, %E)
 - d. total SFA (g, kcal, %E)

Given the number of comparisons, the threshold for a p-value to be considered significant for secondary analyses will be set at 0.003 (Bonferroni adjustment for multiple comparisons).

Descriptive analysis

The exploratory outcome measures (rating scores and open-ended answers from the follow-up questionnaire) will be discussed descriptively.

Descriptives will also include the number and/or proportion of products bought overall, and by food category and demographics, in the two study groups.

Further descriptives will show the number and/or proportion of products bought on promotion in the promotions applied group, by food category, demographics, and depth of promotion.

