1. SYNOPSIS

Study Title	Impact of price promotions on purchases of confectionery and snacks: a randomised controlled trial in an experimental online supermarket study	
Internal ref. no.	N/A	
Study Design	Randomised controlled trial	
Study Participants	Healthy volunteers from the UK	
Planned Sample Size	500	
Planned Study Period	June – December 2021	
	Objectives	Outcome Measures
Primary	To investigate the effect of promotions on the total number of calories selected	Difference in the absolute energy (kcal) of the final basket between the two groups
Secondary	
To investigate the effect of promotions on the nutritional content of the items selected overall, and across the individual target food categories
 
To explore the impact of removing promotions by socioeconomic status
	
Difference in the absolute sugar (g, kcal, %E), salt (g), and saturated fat (g, kcal, %E) of the final basket between the two groups
 
Difference in the absolute energy (kcal), sugar (g, kcal, %E), salt (g), and saturated fat (g, kcal, %E) between the two groups across the individual target food categories
 
Analyses of the primary and secondary outcomes specified above by gender, age group, ethnic group (White vs Non-White), BMI stratified into <30 and ≥ 30kg/m² groups, education level (lower vs. higher), and household income (lower vs. higher)

Exploratory	To investigate the acceptability of the intervention	Rating scores and open-ended answers from the follow-up questionnaire

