9. STATISTICS AND ANALYSIS

9.1. The Number of Participants

There are no previously reported standard deviations of the mean difference from similar trials (e.g. where a one-off shop is done) to guide the estimation of the effect size and standard deviation, and, thus, the calculation of the sample size. However, the study by Brimblecombe *et al.* (25) implemented a complex intervention within real supermarkets in Australia where promotions on high sugar products were removed, including confectionery and sugary drinks. This study found a total reduction of -22% in sales (g/MJ) in confectionery, a difference of -4.5% (SD 15) compared to control; and a reduction of -8% in sugar-sweetened soft drinks, a difference of -13% compared to control.

A total sample of 500 participants (250 in each group) would be needed to detect a minimum effect size of -4.5% in total kcal from the target categories, with 90% power, 5% alpha and 10% attrition.

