16. APPENDIX A: STUDY FLOW CHART

17. APPENDIX B: SCHEDULE OF STUDY PROCEDURES

RECRUITMENT TEXT

The content of the recruitment text will be consistent with other emails sent to panel members but will contain the following text:

Survey topic: Health, Survey length: 10 minutes, Reward: £ xxx

Hi [Name],

We have a new survey available for you. By qualifying and completing this task, you will receive £xxx.

This study is being carried out by the University of Oxford. The study aims to investigate ways of helping people make healthier choices when they shop in an online supermarket. The purpose of this study is to explore how people shop for confectionery and snacks in an online supermarket. It will involve completing an online shopping study which should take no more than 10 minutes.

Before undertaking the task, you will be asked to read some detailed participant information, to confirm you are eligible, and confirm your consent to participate.

For further information and to take part go to [link to survey page (PIS and consent) and shopping website].

SCREENING QUESTIONS (Pre-shopping)

1. Age
 - Under 18 years old
 - 18 years old or over

2. Do you currently reside in the UK?
 - Yes
 - No

3. Are you fluent in English?
 - Yes
 - No

4. Do you have any dietary restrictions?
 - Vegan
 - Gluten-free
 - Sugar-free
 - Dairy/lactose-free
 - None
 - Rather not say

5. Are you the main (or shared) grocery shopper for the food that your household eats?

- Yes
- No

BASELINE MEASURES (Socio-demographic, shopping and health measures)

1. Demographic characteristics

- Gender
 - Male
 - Female
 - Other
 - Prefer not to say
- Age (years)
 - Free text (range of 18-99)
 - Prefer not to say
- Ethnicity (UK Census simplified)
 - White
 - Black
 - Asian
 - Mixed
 - Other
 - Prefer not to say
- Weight and height (in units chosen by participant).

2. Household income (total household income before tax)

- Below £15.5K
- Between £15.5K up to and including £25K
- Between £25K and £39K
- £40K or above

3. Household size – “How many people live at your house, including you?”

4. Highest educational level) - “What is the highest education qualification you have achieved?” (categories based on UK census categories)

- None
- Up to 4 GCSE's (Including 1-4 O Levels/CSE/GCSEs (any grades), Foundation Diploma, NVQ level 1, Foundation GNVQ or equivalents)

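### The SAP's single Bonferroni threshold of 0.003 fits a family of about 16 tests, such as one outcome at a time, and does not hold 5% across all the listed secondary analyses together

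*SAP*

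**What the plan says.** The multiplicity rule is one sentence at the end of the SAP's Secondary Analyses section: "the threshold for a p-value to be considered significant for secondary analyses will be set at 0.003 (Bonferroni adjustment for multiple comparisons". It follows two numbered blocks.

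- Block 1 (demographics) fits models "stratified by demographic covariates including gender, age group, ethnic group (White vs Non-White), BMI" (split at 30 kg/m²), "education level (lower vs. higher), and household income (lower vs. higher". The condition is "provided we have sufficient numbers within each subgroup", set at 30 or more.
- Block 2 (food category) will "compare differences in purchasing for each of the individual target categories", of which there are four.

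Both blocks list four outcomes: energy in kcal, then sugar, salt and saturated fat (SFA), each in g, kcal and %E. A separate SAP heading, Secondary Outcomes, lists the last three for the whole basket.

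Protocol section 9.2 lists the same analyses, has no multiplicity rule and leaves the detail to the SAP. The only alpha in either document is in the sample-size text of protocol section 9.1: "with 90% power, 5% alpha and 10% attrition". Age is collected in Appendix B as "Free text (range of 18-99" years, and no cut-points for age groups appear anywhere. Salt is listed in g, kcal and %E in the SAP and in protocol section 9.2, but in g only in the outcome tables of protocol sections 1 and 4.

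**The concern.** A Bonferroni threshold is a family-wise level divided by a number of tests. The SAP states neither, so the protection that 0.003 gives has to be worked out backwards. Because the sentence closes a section containing both blocks and speaks of secondary analyses in general, the literal reading is that it covers at least both blocks as one set.

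If the family is in fact smaller, a secondary result with p below 0.003 would be reported as surviving Bonferroni correction and be read as protected across the whole secondary programme when it is not. The subgroup results are the most exposed. They include education and income, which serve the objective "To explore the impact of removing promotions by socioeconomic status".

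**Working it through.** **Inputs.** Threshold 0.003 (SAP). Family-wise level 5%: an assumption, borrowed from protocol section 9.1. Four food categories and six demographic factors (SAP). Levels are written out for four factors only (ethnicity, BMI, education, income: 8 strata). Two levels each for gender and age group, giving 12 strata, is an assumption.

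**Step 1: the divisor behind 0.003.** 0.05/0.003 = 16.7. To three decimals, 0.05/m gives 0.003 for m = 15 (0.0033) to m = 20 (0.0025). Applied exactly, 0.003 stays within 5% only up to 16 tests: 16 × 0.003 = 4.8%, 17 × 0.003 = 5.1%. If another level was meant, the rounding range for m is 3–4 at 1%, 8–10 at 2.5% and 29–40 at 10%.

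**Step 2: families that reproduce it.**
- Per outcome: 12 strata + 4 categories = 16 (0.05/16 = 0.0031), or 17 with the whole-basket test (0.05/17 = 0.0029).
- Category block with one measure per nutrient: 4 categories × 4 outcomes = 16. With every listed unit the block is 4 × 10 = 40. With g and kcal merged and salt in g only it is 4 × 6 = 24, which needs 0.05/24 = 0.0021.

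**Step 3: the full list as one family.** With k measures (energy included) and s tests per measure in the demographic block, the total is m = (k − 1) + s × k + 4 × k. The first term omits whole-basket energy, which is the primary test. The upper bound on family-wise error is m × 0.003. The last column, 1 − 0.997^m, is what independent tests would give, as a guide only.

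| Count | m | 0.05/m | Upper bound | If independent |
|---|---|---|---|---|
| One test per factor, one measure per nutrient: 3 + 24 + 16 | 43 | 0.00116 | 12.9% | 12.1% |
| 8 strata with written levels, one measure: 3 + 32 + 16 | 51 | 0.00098 | 15.3% | 14.2% |
| 12 strata, one measure: 3 + 48 + 16 | 67 | 0.00075 | 20.1% | 18.2% |
| 12 strata, g and kcal merged, salt in g: 5 + 72 + 24 | 101 | 0.00050 | 30.3% | 26.2% |
| 12 strata, measures of the protocol tables: 7 + 96 + 32 | 135 | 0.00037 | 40.5% | 33.3% |
| 12 strata, SAP as literally listed: 9 + 120 + 40 | 169 | 0.00030 | 50.7% | 39.8% |

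If the threshold was not meant to reach the Secondary Outcomes heading, the first, third and last rows become 40, 64 and 160. Every row needs a threshold below 0.003. Even a 10% level, with its range of 29 to 40, reaches only the leanest count of the two blocks (40).

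**Step 4: could the subgroup-size rule shrink the list enough?** With one measure per nutrient, each qualifying stratum adds 4 tests to the 16 of the category block. Two strata give 16 + 8 = 24, already above 20.

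**The case against.** The strongest reply is that the sponsor used a family for each outcome. That reproduces 0.003 almost exactly, fits the sentence's position after both blocks, and works however the units are counted, since each measure then has its own family. Choosing a family per outcome is a recognised convention, and nothing in the documents demands a pooled one. The threshold is also far stricter than 0.05, and the tests overlap heavily: the demographic factors re-cut the same participants, and the nutrient measures are related.

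Most of this stands. A reader might infer that 0.003 is a calculation error. The documents do not support that, because a sensible family yields it. A reader might also infer that the secondary error rate is 20% or 51%. Those are worst-case bounds for a pooled family that the SAP never declares, and the documents do not allow the correlation to be allowed for.

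What the reply does not do is put the per-outcome family into the SAP. Under that reading energy, sugar, salt and SFA are not corrected against one another. Under the category-only reading the subgroups are not covered at all. In neither case does the sentence's general scope match what the number protects.

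**Conclusion.** The point holds as a mismatch between the threshold and the scope attached to it. At an assumed 5%, 0.003 protects about 16 tests; the secondary analyses taken together number at least 43 when all six factors are tested, and would need 0.0012 or less. The stated range of bounds rests on that 5%, on two levels for gender and age group in the 12-strata counts, and on all strata or factors being analysed.

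The finding concerns only what may be claimed for secondary results. A reader might take the wording of the socioeconomic objective as grounds for calling all the strata exploratory. That objective stands in the Secondary row of the protocol's tables, apart from the Exploratory row, and names socioeconomic status only, so the documents do not settle it.

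The listing of salt in kcal and %E is a separate, plain inconsistency. Salt supplies no energy, and the protocol's own tables give it in g.

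**What to change.** Choose one of two courses and write it into the SAP, with the family, its size and the level.

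1. **One pooled family.** Replace 0.003 with 0.05 divided by the number of distinct tests actually run after the subgroup-size rule, or use Holm over the same set.
2. **One family per outcome.** Keep 0.003 (0.0029 if the whole-basket test is included), say that it applies within each outcome, and do not describe results as corrected across all secondary analyses.

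Under either, define the age groups, since they change the count. Delete salt in kcal and %E from the SAP (Secondary Outcomes and both blocks) and from protocol section 9.2. Do not count g and kcal of the same nutrient as two tests where one is a fixed multiple of the other.

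Treating the strata as exploratory, or reporting %E descriptively, is optional. It is a design choice, because both belong to listed secondary outcomes. If the strata and the extra units were set aside, 3 + 16 = 19 tests would remain, and the threshold should then be 0.05/19 = 0.0026, since 19 × 0.003 = 5.7%.

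**Cost.** Wording only; no new data. Under course 1 fewer secondary results can be called significant. The effect detectable at 80% power, relative to 0.003 and with two-sided tests assumed, is (z + 0.842)/(2.968 + 0.842): z = 3.248 gives 1.07 (43 tests), z = 3.372 gives 1.11 (67) and z = 3.483 gives 1.14 (101), so about 7% to 14% larger. Course 2 costs no power but limits the claim.

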9.2. Analysis of Outcome Measures

Completion of the task will be defined as spending at least £5 on products from the target categories.

Primary Analysis

Linear regression models will compare the total energy (kcal) purchased in the two groups. Any baseline variables (e.g. demographic characteristics) which appear to have been imbalanced between groups will be adjusted in the model.

Secondary Analysis

Linear regression models will compare the (i) total sugar (g, kcal, %E), (ii) total salt (g, kcal, %E) and (iii) total SFA (g, kcal, %E) purchased in the two groups.

Secondary analyses will also compare differences in total energy (kcal), total sugar (g, kcal, %E), total salt (g, kcal, %E) and total SFA (g, kcal, %E) across the individual target categories.

We will also conduct secondary analyses of the primary and secondary outcomes specified above by gender, age group, ethnic group (White vs Non-White), BMI stratified into <30 and ≥ 30 kg/m² groups, education level (lower vs. higher), and household income (lower vs. higher) provided we have sufficient numbers within each subgroup ($n \geq 30$).

Descriptive analysis

The exploratory outcome measures will be discussed descriptively.

A Statistical Analysis Plan will be finalised before conducting the statistical analysis.

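### The fixed 0.003 Bonferroni cut-off for secondary analyses is valid, but Holm's step-down on a stated family would never find less and may find more at the same error rate

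*SAP*

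**What the plan says.** The multiplicity rule is one sentence, placed after the food-category analyses in the Secondary Analyses part of the SAP: "the threshold for a p-value to be considered significant for secondary analyses will be set at 0.003 (Bonferroni adjustment for multiple comparisons"). It is the same cut-off for every test, with no step-down, hierarchy or resampling. The SAP does not give the number of comparisons, the family-wise alpha, or a list of the tests covered.

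The candidate tests are in three places. Under Secondary Outcomes the SAP states "Linear regression models will compare the two groups on" overall sugar, salt and saturated fat, each in three units; the last entry reads "total saturated fat (SFA) (g, kcal, %E"). Under Secondary Analyses it repeats energy and these nutrients within strata of six demographic factors, and again within four food categories.

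Protocol section 9.2 lists the same kinds of comparison ("Secondary analyses will also compare differences in total energy (kcal), total sugar (g, kcal, %E"), and so on) and has no multiplicity rule. The SAP sentence is therefore the whole plan on this point.

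**The concern.** Single-step Bonferroni compares every p-value with alpha/m. Holm's procedure compares the smallest with alpha/m, the next with alpha/(m−1), and so on up to alpha, stopping at the first failure. It keeps every Bonferroni rejection, can add others, and needs no assumption about dependence. A plan that uses the single-step rule gives up those extra rejections and gets no tighter guarantee in return.

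The protocol's secondary objectives concern nutrient content overall and by food category. If promotions change several of these outcomes, the later steps of a step-down procedure are where real effects could be recovered. At stake is the labelling of some secondary results as not significant. The primary energy comparison is not affected.

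**Working it through.** **1. Where 0.003 comes from.** No derivation is given. With alpha 0.05, 0.05/0.003 = 16.7; 0.05/16 = 0.0031 and 0.05/17 = 0.0029. The natural count that fits is 4 food categories × 4 outcomes (energy, sugar, salt, saturated fat, each once) = 16. The total alpha is then 16 × 0.003 = 0.048.

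**2. The tests actually listed.**
- Overall: 3 nutrients × 3 units = 9.
- Food categories: 4 × (1 energy + 9 nutrient measures) = 40.
- Demographic strata: 6 factors × at least 2 strata × 10 measures = at least 120, fewer if a stratum falls below the SAP's minimum of 30.
- Total: 9 + 40 + 120 = at least 169, counting sugar, salt and saturated fat in every unit. 0.05/169 = 0.0003.

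Counting each nutrient in one unit only gives 3 + 16 + 48 = 67, and 0.05/67 = 0.0007. So 0.003 can hold 5% only over a subset of about 16 tests, which the SAP does not identify.

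**3. Inputs for the power comparison.**
- Effect: protocol section 9.1 gives "a difference of -4.5% (SD 15) compared to control", so 4.5/15 = 0.30 SD. It is the only planning effect with an SD in the documents, and the protocol applies it to total kcal. Using it for nutrients is an assumption.
- Sample size: "A total sample of 500 participants (250 in each group) would be needed", "with 90% power, 5% alpha and 10% attrition". This leaves 250 × 0.9 = 225 per arm.
- Correlation between tests: not given; 0, 0.5 and 0.8 assumed, equal for all pairs.
- Two-sided tests: assumed.

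**4. One test at the fixed cut-off.** Noncentrality = 0.30 × √(225/2) = 3.18. The two-sided critical value at 0.003 is 2.968. Power ≈ Φ(3.18 − 2.97) = Φ(0.214) = 58.5%.

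**5. Holm at the same total alpha.** With m = 16 and alpha 0.048, the thresholds are 0.048/16 = 0.0030, 0.048/15 = 0.0032, 0.048/14 = 0.0034, …, 0.048/2 = 0.024, 0.048/1 = 0.048. The first step equals the fixed cut-off, so the chance of at least one rejection is the same. The later steps are more lenient.

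**6. Simulation** (normal test statistics, 60,000 replicates per setting). Average power per true effect:

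| True effects of 16 | Fixed 0.003 | Holm, correlation 0 / 0.5 / 0.8 |
|---|---|---|
| 1 | 58–59% | 58–59% (no change) |
| 4 | 58–59% | 60% / 60% / 60% |
| 8 | 58–59% | 62% / 62% / 62% |
| 16 | 58–59% | 72% / 71% / 69% |

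The gain is 10 to 14 points if all 16 effects are real, 3 to 4 if 8 are, 1 to 2 if 4 are, and none if 1 is. When all 16 are real it shrinks as correlation rises. The chance of at least one true finding is identical for both rules in every setting; for example, it is 86% for both with 4 true effects and correlation 0.5.

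**7. Unused error under correlation.** With no true effects, the family-wise error at 0.003 over 16 tests is 4.7%, 3.4% and 1.9% at correlation 0, 0.5 and 0.8. Holm leaves this slack where it is: its family-wise error in that setting is the same. Only a procedure that models the dependence, such as step-down max-T by resampling, could use it.

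**The case against.** The strongest reply is that pre-specified Bonferroni is valid, simple and conservative, and that preferring a sharper procedure for secondary analyses is a matter of taste. The first half stands: nothing here is an error. The second half does not quite follow, because at equal family and alpha Holm costs no error control.

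A second reply is that equal family and alpha cannot be assumed when the SAP states neither. This also stands, and it shapes the fix. Over the full list of at least 169 tests, 0.003 per test has a Bonferroni bound of 169 × 0.003 = 0.507. Holm at a true 5% over that list would start at 0.0003 and have average power of about 33 to 42%, against 58 to 59% for the present rule. That compares two different error rates, so it does not defeat Holm's dominance. It does mean a reader should not infer that a step-down rule beats the present cut-off whatever family is chosen.

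A third reply is that the scenario is favourable, which is fair.
- The 0.30 SD was planned for total kcal.
- Food categories compete within a £10 limit, so a common high correlation across all 16 tests is not supported.
- Measures in %E need not move with basket size.
- Demographic strata will be smaller than 225 per arm. At an assumed 60 per arm, noncentrality is 0.30 × √30 = 1.64 and power at 0.003 is about 9%, so little is recoverable there.

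Finally, the overall nutrient outcomes have their own heading, Secondary Outcomes, while the cut-off is set for secondary analyses. Whether they face 0.003 at all is unclear.

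**Conclusion.** The point holds as an efficiency improvement. For any stated family and alpha, Holm keeps every Bonferroni rejection and may add more. Its size depends on how many effects are real: with 16 tests, 0.30 SD, 225 per arm and total alpha 0.048, average power rises from about 58% to about 69 to 72% if all 16 are real, 62% if 8 are, 60% if 4 are, and not at all if 1 is. These figures rest on assumed nutrient effects and correlations.

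Two stronger readings are tempting and not supported. One is that real nutrient effects are being missed: the documents give no nutrient effect size or correlation, so the most that can be said is that some may be. The other is that nutrients moving together strengthens the case for Holm. Holm does not use correlation; that argument supports only a resampling step-down.

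**What to change.** In the SAP, before the secondary results are analysed:

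1. List the tests in the family that 0.003 was meant to cover. Say explicitly whether overall sugar, salt and saturated fat are included, and whether the demographic strata are in the family or descriptive.
2. State the family-wise alpha of 0.05.
3. Count versions of a nutrient that differ only by a constant multiplier (g and kcal) once, since they are the same test.
4. Replace the fixed 0.003 with Holm-adjusted p-values judged at 0.05 within that family.

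With 16 tests or fewer, Holm at 0.05 starts at 0.0031 or higher, so every result significant at 0.003 stays significant. With more than 16, 0.003 itself exceeds 0.05/m, and the family-wise bound passes 5%.

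The cost is a short SAP paragraph and one line of code; the thought goes into naming the family. A small downside is that Bonferroni has matching simultaneous intervals (99.7% at this cut-off), while Holm has no equally simple ones. Unadjusted 95% intervals could be shown and labelled as such. Step-down max-T by permuting the arm label is optional. It could use the correlation between outcomes, but would need adapting to covariate-adjusted models and overlapping strata.
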